12.5. Appendix 5: Derived and Transformed Data

12.5.1. General

Multiple Measurements at One Analysis Time Point

 Where multiple assessments are made, the mean of replicate assessments at any given time point will be used as the value for that time point. This derived mean will be reported in the listing in addition to the individual assessments. If there are two values within a time window, the value closest to the target day for that window will be used. If values are the same distance from the target, then the mean will be taken. Participants having both High and Low values for Normal Ranges at any post-baseline visit for safety parameters will be counted in both the High and Low categories of "Any visit post-baseline" row of related summary tables. This will also be applicable to relevant Potential Clinical Importance summary tables.
Study Day

 Calculated as the number of days from Dose Date: 
 Ref Date = Missing → Study Day = Missing Ref Date < Dose Date → Study Day = Ref Date – Dose Date Ref Date ≥ Dose Date → Study Day = Ref Date – (Dose Date) + 1

12.5.2. Study Population

Cumulative Dose
Placebo: 0
GSK2330811: Number of Injections x 150
Dose unit: Milligram
Demographics
Age

 Only birth year is captured on the eCRF, therefore GSK standard ISDL algorithms will be used for calculating age where birth date will be imputed as follows: The missing date and month will be imputed as '30th June' Birth date will be presented in listings as 'YYYY'
Body Mass Index (BMI)

 Calculated as Weight(kg)/Height(m)²

12.5.3. Safety

ECG Parameters
RR Interval
If RR interval (msec) is not provided directly, then RR can be derived using machine read QTcF as:

$$RR = \left[\left(\frac{QT}{QTcF} \right)^3 \right] * 1000$$

CONFIDENTIAL

208564

Laboratory Parameters

- If a laboratory value which is expected to have a numeric value for summary purposes, has a non-detectable level reported in the database, where the numeric value is missing, but typically a character value starting with '<x' or '>x' (or indicated as less than x or greater than x in the comment field) is present, the number of decimal places in the observed values will be used to determine how much to add or subtract in order to impute the corresponding numeric value.
 - Example 1: 2 decimal places: '< x' becomes $x - 0.01$
 - Example 2: 1 decimal places: '> x' becomes $x + 0.1$
 - Example 3: 0 decimal places: '< x' becomes $x - 1$.

CONFIDENTIAL

208564

12.6. Appendix 6: Reporting Standards for Missing Data

12.6.1. Premature Withdrawals

Element	Reporting Detail
General	
 Participant study completion (i.e. as specified in the protocol) was defined as completion of all assessment on Day 126. A maximum of 4 non-evaluable participants will be replaced. All available data from participants who were withdrawn from the study will be listed and all available planned data will be included in summary tables and figures, unless otherwise specified. Withdrawal visits will be slotted as per Appendix 2: Assessment Windows or will be summarised as withdrawal visits.

12.6.2. Handling of Missing Data

Element	Reporting Detail
General	
 Missing data occurs when any requested data is not provided, leading to blank fields on the collection instrument: 
 These data will be indicated by the use of a “blank” in subject listing displays. Unless all data for a specific visit are missing in which case the data is excluded from the table. Answers such as “Not applicable” and “Not evaluable” are not considered to be missing data and should be displayed as such.
Outliers	
 Any participants excluded from the summaries and/or statistical analyses will be documented along with the reason for exclusion in the clinical study report.

12.6.2.1. Handling of Missing and Partial Dates

Element	Reporting Detail
General	
 Partial dates will be displayed as captured in subject listing displays.
Adverse Events	
 In case of partial dates (i.e. day missing, only month and year present) recorded for AE start and end, the following conventions will be applied for calculating the time to onset and the duration of the event: 
 Missing Start Day: First of the month will be used unless this is before the start date of study treatment; in this case the study treatment start date will be used and hence the event is considered On-treatment as per Appendix 3: Study Phases and Treatment Emergent Adverse Events. Missing Stop Day: If the partial date is a stop date, a '28/29/30/31' will be used for the day (dependent on the month and year) and 'Dec' will be used for the month. Completely missing start or end dates will remain missing, with no imputation applied. Consequently, time to onset and duration of such events will be missing.
Concomitant Medications/ Medical History	
 Partial dates for any concomitant medications recorded in the CRF will be imputed using the following convention: 
 If the partial date is a start date, a '01' will be used for the day and 'Jan' will be used for the month If the partial date is a stop date, a '28/29/30/31' will be used for the day (dependent on the month and year) and 'Dec' will be used for the month. The recorded partial date will be displayed in listings.

CONFIDENTIAL

208564

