8.3.1. Time Period and Frequency for Collecting AE and SAE Information

- All SAEs will be collected from the signing of the ICF until the final follow-up visit.
- All AEs will be collected from the start of intervention until the final follow-up visit (Section 1.3).
- Medical occurrences that begin before the start of study intervention but after obtaining informed consent will be recorded on the Medical History/Current Medical Conditions section of the CRF not the AE section. The exceptions are SAEs, which must be recorded in the CRF AE/SAE section.
- All SAEs will be recorded and reported to the sponsor or designee immediately and under no circumstance should this exceed 24 hours, as indicated in [Appendix 3](#). The investigator will submit any updated SAE data to the sponsor within 24 hours of it being available.
- Investigators are not obligated to actively seek AEs or SAEs after the conclusion of the study participation. However, if the investigator learns of any SAE, including a death, at any time after a participant has been discharged from the study, and he/she considers the event to be reasonably related to the study intervention or study participation, the investigator must promptly notify the sponsor.

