12.3.1.1. Study Phases for Concomitant Medication

Study Phase	Definition
Prior	If medication end date is not missing and is prior to study treatment
Concomitant	Any medication that is not a prior

NOTES:

- Please refer to [Appendix 6](#): Reporting Standards for Missing Data for handling of missing and partial dates for concomitant medication. Use the rules in this table if concomitant medication date is completely missing.

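### Read literally, the AE partial-date rule in SAP 12.6.2.1 replaces a recorded stop month with December, and the medication rule lacks the condition that would prevent the same thing

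*SAP*

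**What the plan says.** **AE row, SAP 12.6.2.1.** The scope is set by the opening words: "In case of partial dates (i.e. day missing, only month and year present) recorded for AE start and end". The "conventions will be applied for calculating the time to onset and the duration of the event".

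- *Stop date:* under the Missing Stop Day bullet, 28, 29, 30 or 31 "will be used for the day (dependent on the month and year) and 'Dec' will be used for the month".
- *Start date:* "First of the month will be used unless this is before the start date of study treatment", in which case the treatment start date is used.
- AE dates that are wholly missing stay missing.

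**Medication row, same section.** "Partial dates for any concomitant medications recorded in the CRF will be imputed using the following convention". The stop-date wording matches the AE row. The start-date wording sets the day to the first and the month to January. Neither is limited to dates with no recorded month.

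**Use of the medication dates.** SAP 12.3.1.1 sends partial dates to Appendix 6 (SAP 12.6). It classes a medication as prior "If medication end date is not missing and is prior to study treatment", and as concomitant "Any medication that is not a prior". Table 1.11 summarises concomitant medications in the Safety population.

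**Collection period.** Protocol 8.3.1: "All AEs will be collected from the start of intervention until the final follow-up visit". Protocol 4.3 puts expected participation at no more than 163 days.

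**The concern.** Every AE stop date within the stated scope has a known month, so an instruction to set the month discards recorded data. A programmer who follows the text would turn a short event in the first half of the year into one lasting most of that year, well past the final visit.

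In the medication row the same sentence can carry a drug that was certainly stopped before dosing to 31 December of the dosing year, and so from prior to concomitant. With about 7 active and 3 placebo participants, one misclassified participant moves a table percentage by 1/7 = 14 points or 1/3 = 33 points.

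**Working it through.** **1. Benchmark.** Screening of up to 30 days, a final visit on Day 126 and a 7-day window (Protocol 1.3 and 4.1) give 30 + 126 + 7 = 163 days, which reproduces the figure in Protocol 4.3. The last possible scheduled day of AE collection is 126 + 7 = Day 133.

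**2. Internal consistency.** If the month is always December, the day is always 31, and neither the choice of 28/29/30/31 nor its dependence on month and year has any purpose. The AE start-date rule keeps the recorded month; the stop-date rule, on its face, does not.

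**3. Shift per month.** Shift = 31 December of the recorded year minus the last day of the recorded month. For January 2020 this is 366 − 31 = 335 days (2019: 365 − 31 = 334).

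| Recorded stop month (2020) | Shift, days |
|---|---|
| Jan | 335 |
| Feb | 306 |
| Mar | 275 |
| Apr | 245 |
| May | 214 |
| Jun | 184 |
| Jul | 153 |
| Aug | 122 |
| Sep | 92 |
| Oct | 61 |
| Nov | 31 |
| Dec | 0 |

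Taking the day number from the recorded month instead of 31 changes these by at most 3 days.

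**4. Example (assumed dates; the documents give no dosing dates).** Dosing 3 February 2020, AE onset 10 February, stop recorded as February 2020. As written, the stop is 31 December 2020, which is study day 333, and the duration is 326 days. Keeping the month, the stop is 29 February and the duration is 20 days. Day 133 would be 14 June 2020.

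**5. How often the AE result runs past follow-up.** Take a true 7-day AE with the stop day missing, any onset that lets it end by Day 133, and dosing on each day of an assumed period:

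| | Dosing Jan–Dec 2020 | Dosing Oct 2019–Mar 2020 |
|---|---|---|
| Imputed stop after Day 133, as written | 82.5% | 83.9% |
| Same, month end | 11.6% | 11.5% |
| Duration over 133 days, as written | 65.3% | 83.9% |
| Same, month end | 0% | 0% |
| Duration over 163 days, as written | 57.1% | 83.5% |

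**6. Medications.** Suppose a drug was stopped *d* days before dosing, the stop day is missing, and dosing falls on any day of 2020.

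- As written, it is concomitant whenever the stop is in the dosing calendar year: (366 − *d*)/366.
- With month end, it is concomitant only when the stop is in the dosing month: (366 − 12*d*)/366 for *d* up to 29. At *d* = 30 only the seven 31-day months contribute, giving 7/366.
- The difference is the misclassification due to the wording.

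| *d* | As written | Month end | Difference |
|---|---|---|---|
| 7 | 359/366 = 98.1% | 282/366 = 77.0% | 77/366 = 21.0% |
| 14 | 352/366 = 96.2% | 198/366 = 54.1% | 154/366 = 42.1% |
| 20 | 346/366 = 94.5% | 126/366 = 34.4% | 220/366 = 60.1% |
| 30 | 336/366 = 91.8% | 7/366 = 1.9% | 329/366 = 89.9% |

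Examples: a stop of January 2020 with dosing on 15 March 2020 becomes 31 December 2020 and concomitant, although the drug was certainly stopped before dosing. A stop of November 2019 with the same dosing date becomes 31 December 2019 and stays prior. The January start-date rule does not affect the phase, because SAP 12.3.1.1 uses only the end date.

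**The case against.** **Intent.** The wording makes sense component by component: a missing day takes the last day of the month, a missing month takes December. The bullet is headed Missing Stop Day and its start-date partner keeps the month. This is persuasive about what was meant, and it makes a drafting slip far more likely than a deliberate choice. It does not rescue the AE text, whose scope leaves no date with a missing month for December to apply to.

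**Medication row.** That row covers any partial date, including year-only dates, where January and December are ordinary choices. This stands in full: the fault there is only the missing condition. Stops in an earlier calendar year than dosing are also unaffected.

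**Exposure.** Protocol 6.5 requires recording of medication taken at enrolment or during the study, with review from screening, at most 30 days before Day 1. Drugs stopped months before dosing are largely outside required collection, which is why the table above ends at 30 days. Month-end imputation also leaves a drug stopped in the dosing month as concomitant; with the day unknown, no rule can settle that case from the date alone.

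**A stronger reading.** A reader might infer that every day-missing stop date gives an impossible duration. The documents do not support that. The shift is zero for December and modest in late autumn, and SAE follow-up may continue past the final visit (Protocol 4.3 and 8.3.3).

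**Conclusion.** The AE stop-date sentence, followed literally, gives a wrong result for any recorded month other than December: 31 to 335 extra days of derived duration, often beyond the AE collection period. The medication sentence is incomplete. It misclassifies a day-missing stop in an earlier month of the dosing calendar year and can inflate Table 1.11.

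Severity is low. A reader might also infer that the safety results are distorted, but the plan does not support this. The primary endpoints are participant counts, the treatment-emergent flag uses the AE start (SAP 12.3.2), partial dates are listed as captured, and no planned safety table has AE duration in its title (SAP 12.9.5). Whether a derived duration appears in the AE listings cannot be seen, because the standard shells are cited only by code.

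The shifts in days follow from the calendar. The percentages rest on assumed dosing dates and on a 7-day AE. The number of partial dates is unknown; with about ten participants at one centre it is probably small.

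**What to change.** In SAP 12.6.2.1:

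- **AE stop dates, day missing:** use the last day of the recorded month, capped at the participant's date of last contact. Delete the reference to December.
- **AE start dates:** leave unchanged, including the provision that substitutes the treatment start date. A plain first-of-month rule would drop that provision and could date an event from the dosing month before dosing.
- **Medications, day missing only:** use the first (start) or last (stop) day of the recorded month.
- **Medications, day and month missing:** use 1 January (start) or 31 December (stop) of the recorded year.

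The cost is a few sentences in Appendix 6 and a check of the date-imputation code. Data collection and the protocol do not change.

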12.6.2.2. Imputation of Missing Data for OSM Free and Total

Element	Reporting Detail
LLQ/2	
 • If data are missing due to readings being below the limits of quantification, then a value equivalent to LLQ/2 will be imputed. • If the readings are above the upper limit of quantification, the sample should be further diluted to be within the upper limit of quantification of the assay. The measured concentration should then be corrected for the additional dilution factor. • These values will be used for the computation of the change from baseline and for summaries, plots and analysis, if deemed applicable. • The number of data imputed will be highlighted in the summaries and figures, whereas listings will report the values as below LLQ. • The numeric values and LLQ will be presented in listing as a reference, and the LLQ will be mentioned in footnotes where appropriate (e.g. figures).

CONFIDENTIAL

208564

12.7. Appendix 7: Values of Potential Clinical Importance

12.7.1. Laboratory Values

Haematology and chemistry parameters will use CTCAE grades (CTCAE criteria, V5.0: November 27, 2017) to highlight important results based on laboratory value only (i.e. no clinical judgement will be applied). CTCAE grades will replace the category of “values of potential clinical importance” for haematology parameters, see table below for reference.

Laboratory Parameter	CTCAE v5.0 Term for Adverse Event	Grade 1	Grade 2	Grade 3	Grade 4	Grade 5
Haemoglobin	Anemia	Hemoglobin (Hgb) <LLN - 100 g/L	Hgb <100 - 80g/L	Hgb <80 g/L; transfusion indicated	Life-threatening consequences; urgent intervention indicated	Death
Haemoglobin	Hemoglobin increased	Increase in >0 - 2 g/dL above ULN or above baseline if baseline is above ULN	Increase in >2 - 4 g/dL above ULN or above baseline if baseline is above ULN	Increase in >4 g/dL above ULN or above baseline if baseline is above ULN	-	-
Lymphocyte count	Lymphocyte count decreased	<LLN - 0.8 GI/L	<0.8 - 0.5 GI /L	<0.5 - 0.2 GI /L	<0.2 GI /L	-
Lymphocyte count	Lymphocyte count increased	-	>4 – 20 GI/L	>20 GI/L	-	-
Neutrophil count	Neutrophil count decreased	<LLN - 1.5 GI /L	<1.5 - 1.0 GI /L	<1.0 - 0.5 GI /L	<0.5 GI/L	-
Platelet count	Platelet count decreased	<LLN - 75.0 GI /L	<75.0 - 50.0 GI /L	<50.0 - 25.0 GI /L	<25.0 GI/L	-
White blood cell count	Leukocytosis	-	-	>100 GI/L	Clinical manifestations of leucostasis; urgent intervention indicated	Death
White blood cell count	White blood cell	<LLN - 3.0 GI /L	<3.0 - 2.0 GI /L	<2.0 - 1.0 GI /L	<1.0 GI /L	-

CONFIDENTIAL

208564

Laboratory Parameter	CTCAE v5.0 Term for Adverse Event	Grade 1	Grade 2	Grade 3	Grade 4	Grade 5
	decreased					
Alanine Amino Transferase (IU/L)	Alanine aminotransferase increased	>ULN - 3.0 x ULN if baseline was normal; 1.5 - 3.0 x baseline if baseline was abnormal	>3.0 - 5.0 x ULN if baseline was normal; >3.0 - 5.0 x baseline if baseline was abnormal	>5.0 - 20.0 x ULN if baseline was normal; >5.0 - 20.0 x baseline if baseline was abnormal	>20.0 x ULN if baseline was normal; >20.0 x baseline if baseline was abnormal	
Aspartate Amino Transferase (IU/L)	Aspartate aminotransferase increased	>ULN - 3.0 x ULN if baseline was normal; 1.5 - 3.0 x baseline if baseline was abnormal	>3.0 - 5.0 x ULN if baseline was normal; >3.0 - 5.0 x baseline if baseline was abnormal	>5.0 - 20.0 x ULN if baseline was normal; >5.0 - 20.0 x baseline if baseline was abnormal	>20.0 x ULN if baseline was normal; >20.0 x baseline if baseline was abnormal	
Calcium (MMOL/L)	Hypocalcemia	Corrected serum calcium of <LLN - 2.0 mmol/L; ionized calcium <LLN - 1.0 mmol/L	Corrected serum calcium of <2.0 - 1.75 mmol/L; ionized calcium <1.0 - 0.9 mmol/L; symptomatic	Corrected serum calcium of <1.75 - 1.5 mmol/L; ionized calcium <0.9 - 0.8 mmol/L; hospitalization indicated	Corrected serum calcium of; <1.5 mmol/L; ionized calcium <0.8 mmol/L; life-threatening consequences	Death
Cholesterol	Cholesterol - high	>ULN - 7.75 mmol/L	>7.75 - 10.34 mmol/L	>10.34 - 12.92 mmol/L	>12.92 mmol/L	
Creatinine	Creatinine increased	>ULN - 1.5 x ULN	>1.5 - 3.0 x baseline; >1.5 - 3.0 x ULN	>3.0 x baseline; >3.0 - 6.0 x ULN	>6.0 x ULN	
Glucose	Hyperglycemia	Abnormal glucose above baseline with no medical intervention	Change in daily management from baseline for a diabetic; oral antiglycemic agent initiated;	Insulin therapy initiated; hospitalization indicated	Life-threatening consequences; urgent intervention indicated	Death

CONFIDENTIAL

208564

Laboratory Parameter	CTCAE v5.0 Term for Adverse Event	Grade 1	Grade 2	Grade 3	Grade 4	Grade 5
			workup for diabetes			
Glucose	Hypoglycemia	<LLN - 3.0 mmol/L	<3.0 - 2.2 mmol/L	<2.2 - 1.7 mmol/L	<1.7 mmol/L; life threatening consequences; seizures	Death
Potassium	Hyperkalemia	>ULN - 5.5 mmol/L	>5.5 - 6.0 mmol/L; intervention initiated	>6.0 - 7.0 mmol/L; hospitalization indicated	>7.0 mmol/L; life-threatening consequences	Death
Potassium	Hypokalemia	<LLN - 3.0 mmol/L	Symptomatic with <LLN - 3.0mmol/L; intervention indicated	<3.0 - 2.5 mmol/L; hospitalization indicated	<2.5 mmol/L; life-threatening consequences	Death
Sodium	Hypernatremia	>ULN - 150 mmol/L	>150 - 155 mmol/L; intervention initiated	>155 - 160 mmol/L; hospitalization indicated	>160 mmol/L; life-threatening consequences	Death
Sodium	Hyponatremia	<LLN - 130 mmol/L	125-129 mmol/L and asymptomatic; 120-124 mmol/L regardless of symptoms	125-129 mmol/L symptomatic; 120-124 mmol/L regardless of symptoms	<120 mmol/L; life-threatening consequences	Death
Total Bilirubin	Blood bilirubin increased	>ULN - 1.5 x ULN if baseline was normal; > 1.0 - 1.5 x baseline if baseline was abnormal	>1.5 - 3.0 x ULN if baseline was normal; >1.5 - 3.0 x baseline if baseline was abnormal	>3.0 - 10.0 x ULN if baseline was normal; >3.0 - 10.0 x baseline if baseline was abnormal	>10.0 x ULN if baseline was normal; >10.0 x baseline if baseline was abnormal	Death
Triglycerides	hypertriglyceridemia	1.71 mmol/L - 3.42 mmol/L	>3.42 mmol/L - 5.7 mmol/L	>5.7 mmol/L - 11.4 mmol/L	>11.4 mmol/L; life-threatening consequences	Death

CONFIDENTIAL

208564

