12.9.5. Safety Tables

Safety: Tables					
No.	Population	IDSL / Example Shell	Title	Programming Notes	Deliverable [Priority]
Adverse Events (AEs)					
3.1.	Safety	AE1	Summary of All Adverse Events by System Organ Class and Preferred Term		SAC
3.2.	Safety	AE5A	Summary of Adverse Events by System Organ Class and Preferred Term and Maximum Intensity		SAC
3.3.	Safety	AE1	Summary of Drug-Related Adverse Events by System Organ Class and Preferred Term		SAC
3.4.	Safety	AE15	Summary of Non-serious Adverse Events by System Organ Class and Preferred Term (Number of Subjects and Occurrences)		SAC
Serious and Other Significant Adverse Events					
3.5.	Safety	AE16	Summary of Serious Adverse Events by System Organ Class and Preferred Term (Number of Subjects and Occurrences)		SAC
3.6.	Safety	AE3	Summary of Serious Drug-Related Adverse Events by Overall Frequency		SAC
3.7.	Safety	AE1	Summary of Adverse Events Leading to Permanent Discontinuation of Study Treatment or Withdrawal from Study by System Organ Class and Preferred Term		SAC
Chemistry					
3.8.	Safety	LB1	Summary of Chemistry		SAC
3.9.	Safety	LB17	Summary of Worst-Case Chemistry Results Relative to Potential Clinical Importance (PCI) Criteria Post-Baseline Relative to Baseline		SAC

CONFIDENTIAL

208564

Safety: Tables					
No.	Population	IDSL / Example Shell	Title	Programming Notes	Deliverable [Priority]
3.10.	Safety	SAFE_T1	Summary of Chemistry Results by Maximum CTCAE Grade	Footnote: "CTCAE criteria, V5.0: November 27, 2017"	SAC
Haematology					
3.11.	Safety	LB1	Summary of Haematology	By parameter	SAC
3.12.	Safety	LB16	Summary of Haematology Results by Maximum CTCAE Grade Increase Post-Baseline Relative to Baseline	Footnote: "CTCAE criteria, V5.0: November 27, 2017"	SAC
3.13.	Safety	LB17	Summary of Worst Case Haematology Results Relative to Potential Clinical Importance (PCI) Criteria Post-Baseline Relative to Baseline		SAC
3.14.	Safety	SAFE_T2	Summary of Nadirs for Selected Haematology Parameters	By parameter, treatment group Produce for Platelet count and Haemoglobin. Footnote: "Nadir is the lowest post-baseline value of the parameter"	SAC
3.15.	Safety	SAFE_T3	Summary of Days to Nadir of Selected Haematology Parameters	by parameter, treatment group. Produce for Platelet count and Haemoglobin. Footnote: "Nadir is the lowest post-baseline value of the parameter"	SAC

CONFIDENTIAL

208564

Safety: Tables					
No.	Population	IDSL / Example Shell	Title	Programming Notes	Deliverable [Priority]
Urinalysis					

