12.10. Appendix 10: Example Mock Shells for Data Displays

Example: SAFE T1

Protocol: 208564

Population: Safety

Page 1 of n

Table XX.XX
Summary of Chemistry Results by Maximum CTCAE Grade

Test: Creatinine (UMOL/L)

Event: Creatinine increased

Treatment	N	Grade 1	Grade 2	Grade 3	Grade 4
Placebo	XX	XX	XX.X	XX.XX	XX.X
GSK2330811 450 mg	XX	XX	XX.X	XX.XX	XX.X

Note: CTCAE criteria, V5.0: November 17, 2017 graded on laboratory test value.

Only events with at least one graded value are shown.

CONFIDENTIAL

208564

Example: SAFE_T2

Protocol: 208564

Population: Safety

Page 1 of n

Table XX.XX

Summary of Nadirs for Selected Haematology Parameters [as Percent Change from Baseline]

Lab Test (unit)	Treatment	N	n	Mean	SD	Median	Min	Max
Hemoglobin (G/L)	Placebo	XX	XX	XX.X	XX.XX	XX.X	XX.X	XX.X
	GSK2330811 450 mg	XX	XX	XX.X	XX.XX	XX.X	XX.X	XX.X

.....

Note: Nadir is the lowest post-baseline value of the parameter.

CONFIDENTIAL

208564

Example: SAFE_T3

Protocol: 208564

Population: Safety

Page 1 of n

Table XX.XX
Summary of Days to Nadir for Selected Haematology Parameters

Lab Test (unit)	Treatment	N	n	Median	Min	Max	Range
Hemoglobin (G/L)	Placebo	XX	XX	XX	XX	XX	XX
	GSK2330811 450 mg	XX	XX	XX	XX	XX	XX

.....

Note: Nadir is the lowest post-baseline value of the parameter.

CONFIDENTIAL

208564

Example: SAFE_T4

Programming note: please flag to study team/ statistics when summarizing if observe any character variables not the minimum value and not presented as an increase category.

Tests to summarise as X=BACTM_URQ (minimum value=NONE SEEN)

Tests to summarise as Y= BLD_URC, PROT_URG, KETO_URG, GLUC_URG (minimum value=NEGATIVE)

Tests to summarise as Z= RBCM_URG, WBCM_URG (minimum value=NONE SEEN)

Tests to summarise as W= SG_URG (minimum value=Low)

Example modified from UR1

Protocol: ABC123456

Page 1 of 1

Population: Safety/Other study specific

Table X
Summary of Worst Case Urinalysis Results Post-Baseline Relative to Baseline

Test	n	Treatment A (N=248)		Treatment B (N=247)	
X		230		232	
	No Change/Decreased	222 (97%)		223 (96%)	
	Any Increase	8 (3%)		9 (4%)	
	Increase to MANY	6 (3%)		5 (2%)	
Y	n	230		232	
	No Change/Decreased	222 (96%)		222 (96%)	
	Any Increase	7 (3%)		10 (4%)	
	Increase to TRACE	2 (<1%)		5 (2%)	
	Increase to 1+	1 (<1%)		4 (2%)	
	Increase to 2+	1 (<1%)		0	
	Increase to 3+	4 (2%)		1 (<1%)	
Z	n	230		232	
	No Change/Decreased	222 (96%)		222 (96%)	
	Any Increase	7 (3%)		10 (4%)	
	Increase to 0-1	2 (<1%)		5 (2%)	

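### Under value-only CTCAE grading, sodium 120-129 mmol/L and potassium from 3.0 mmol/L to below LLN have no unique grade, and sodium 120-124 is listed outright in both Grade 2 and Grade 3

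*SAP*

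**What the plan says.** SAP 12.7.1 applies CTCAE v5.0 to haematology and chemistry "based on laboratory value only (i.e. no clinical judgement will be applied". The rows that matter here are:

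| Row | Grade 1 | Grade 2 | Grade 3 |
|---|---|---|---|
| Hyponatremia | "<LLN - 130 mmol/L" | "125-129 mmol/L and asymptomatic; 120-124 mmol/L regardless of symptoms" | "125-129 mmol/L symptomatic; 120-124 mmol/L regardless of symptoms" |
| Hypokalemia | "<LLN - 3.0 mmol/L" | "Symptomatic with <LLN - 3.0mmol/L; intervention indicated" | 2.5 to below 3.0 mmol/L |

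Grade 4 is sodium below 120 and potassium below 2.5 mmol/L.

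The grades feed Table 3.10, "Summary of Chemistry Results by Maximum CTCAE Grade" (SAP 12.9.5), whose mock shell in SAP 12.10 says results are "graded on laboratory test value". They also feed Listing 20, the graded haematology and chemistry values. The related primary endpoint (SAP 2.2) counts participants with any laboratory result at Grade 1 or above. Neither document says what to do when one value fits two grades, or how to treat clauses that depend on symptoms.

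**The concern.** A rule that uses only the number needs exactly one grade for each number. Two rows fail this, for different reasons.

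- **Sodium 120-124 mmol/L.** The same band, on the same terms, stands under Grade 2 and Grade 3. Symptom data would not separate them.
- **Sodium 125-129 mmol/L, and potassium from 3.0 mmol/L to below LLN.** Each band appears under two grades that are told apart only by symptoms or intervention, which the rule sets aside.

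Two programmers following the SAP could therefore place the same participant in different columns of Table 3.10, and neither would have departed from the text. Laboratory grading belongs to the primary safety objective. The table takes the maximum over 12 scheduled post-dose chemistry timepoints from Day 2 to Day 126 (SAP 12.2.1) plus unscheduled visits, so a single borderline value is enough to set a participant's entry.

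**Working it through.** The plan gives no figure to reproduce. The check is to read the two rows as written and list every grade that each value satisfies.

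**Inputs.** The bands come from SAP 12.7.1. The documents give no LLN, so I assume sodium 135 mmol/L (range 133 to 136) and potassium 3.5 mmol/L (range 3.4 to 3.6). Sodium is stepped by 1 mmol/L and potassium by 0.1 mmol/L.

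**Values that match two grades**

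| Analyte | Symptoms not used (the SAP rule) | Known absent | Known present |
|---|---|---|---|
| Sodium | 120 to 129: 10 values, Grades 2 and 3 | 120 to 124: 5 values | 120 to 124: 5 values |
| Potassium, LLN 3.5 | 3.0 to 3.4: 5 values, Grades 1 and 2 | none | 3.0 to 3.4: 5 values |

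The sodium result is the same for every LLN from 133 to 136. For potassium the number of double matches is 4 at LLN 3.4 and 6 at LLN 3.6. The last potassium cell arises because a symptomatic value still satisfies the Grade 1 wording as well.

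**Lowest against highest matching grade**

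- Potassium 3.2: 1 or 2
- Sodium 128: 2 or 3
- Sodium 122: 2 or 3
- Unambiguous for comparison: sodium 132 is Grade 1 and 118 is Grade 4; potassium 2.8 is Grade 3 and 2.4 is Grade 4

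Each affected value shifts by exactly one grade. Both candidate grades are at least 1, so the count at Grade 1 or above is the same whichever is taken. The flags in SAP 12.7.2 (sodium 130 and 150, potassium 3 and 5.5) use their own cut-offs and are untouched. The hypernatremia and hyperkalemia bands do not overlap.

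**Which grade fits sodium 120-124.** Suppose it were Grade 2 whatever the symptoms. A symptomatic participant at 122 would then be Grade 2, while a symptomatic participant at 127 would be Grade 3, so the lower sodium would get the milder grade. With 120-124 in Grade 3, grades never fall as sodium falls, with or without symptoms. Only Grade 3 keeps the row in order.

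**After one band per grade.** Double matches fall from 10 to 0 for sodium and from 5 to 0 for potassium (from 4 to 6 down to 0 over the LLN range).

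**The case against.** The best reply is that potassium Grade 2 is a joint condition. A number alone cannot show symptoms, so the natural value-only reading is Grade 1 and nothing is ambiguous. That is a sensible reading, and it is the one the fix adopts. But it is not written down, and it does not carry over to sodium. Striking the symptom words leaves 125-129 in both Grade 2 and Grade 3. Striking the whole clauses leaves 125-129 with no grade. Neither helps 120-124.

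A reader might go the other way and infer that, because Table 3.10 reports a maximum, every slightly low potassium will appear as Grade 2 and every sodium of 125-129 as Grade 3. The documents do not support that. The title reads most naturally as each participant's worst grade over time. Taking the highest of several cells matched by one value is a different operation, which the SAP neither prescribes nor forbids. The text supports only that such values could be shown a grade higher.

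It is also fair to say that the outright contradiction has little practical reach, since sodium of 120-124 is unlikely in healthy volunteers, while the realistic case, slightly low potassium, is the one a careful programmer would probably settle at Grade 1. No hypothesis is tested, and the listings let a reader check individual values. All of this stands, and it limits the importance of the point without making the table consistent.

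**Conclusion.** The point holds as a minor but real defect in an operative rule. On value alone, sodium 120-129 mmol/L and potassium from 3.0 mmol/L to below LLN have no unique grade, and the double entry at sodium 120-124 is a contradiction under any reading. The effect is at most one grade per affected value, confined to Table 3.10 and Listing 20. The primary count and the potential-clinical-importance flags are unaffected, provided one of the two matching grades is assigned.

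Two further inferences should be resisted. First, the error does not always run upwards. For a symptom-free participant with potassium just below LLN or sodium of 125-129, the risk is a grade too high; at sodium 120-124, the ordering of the row makes it a grade too low. Second, one participant is 1/7 = 14% of a seven-person active arm, but that is true of any single event and says nothing about how likely this one is.

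The potassium counts rest on the assumed LLN. The placement of 120-124 in Grade 3 rests on the internal order of the row; the cited CTCAE text was not available to check.

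**What to change.** Make these changes in SAP 12.7.1 before unblinding for the final analysis:

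1. Reconcile the 120-124 mmol/L entry with the cited CTCAE v5.0 table by removing the Grade 2 copy, so that the band stands only under Grade 3.
2. Add one sentence: where two grades share a numeric band and differ only by symptoms or intervention, value-only grading assigns the lower grade. Potassium from 3.0 mmol/L to below LLN is then Grade 1, and sodium 125-129 mmol/L is Grade 2.
3. Repeat that convention as a footnote to Table 3.10.

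The cost is one deletion, one sentence and one footnote, with no new data. The small downside is that a symptomatic participant in these bands is graded on the number alone. The symptoms themselves are still captured through adverse event reporting.
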